Total sample size. Based on the analyses described above, we would need 106 participants per group to detect effects between the pairs of groups for the planned comparisons. After adjusting for the anticipated rates of missing data (15% missing), we need to randomize 125 participants to each of the three groups to ensure that we have sufficient sample sizes (125 participants x 0.85 collected assessments = 106 participants per group). Thus, we will randomize a total of 375 participants.

d. Early stopping rules.

The study investigators and a Data Monitoring Committee (DMC) will provide data and safety monitoring of the proposed trial. To monitor adverse events, all staff members who have regular contact with study participants are instructed on the need to report to an investigator any indication that an adverse event has occurred. When the staff members and investigators learn of an adverse event, they will investigate until they have determined as many of the relevant details of the adverse event as possible. To provide consistent monitoring of adverse events across groups, participants will be asked about all categories of adverse events at each routine assessment visit conducted throughout the study. At least one investigator will review each adverse event as it occurs. The DMC will review a summary of adverse events annually. This frequency of review will be increased if the adverse events occur at a higher rate than anticipated. The protocol can be stopped based on recommendations of the investigators or DMC who are reviewing the adverse events in the study. We will ask the investigators and DMC to recommend that the trial be stopped if a review of the adverse events suggests to any of the investigators or DMC members that the number of related adverse events is unacceptably high. The investigators or DMC will be allowed to request statistical analyses to compare the groups on the rates of different adverse events or to have the adverse event data summarized in other ways that they deem appropriate.

8. Risks

a. Medical risks, listing all procedures, their major and minor risks and expected frequency.

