This study involves the development and evaluation of a behavioral intervention to promote adherence to an FDA-approved medication (buprenorphine) for opioid use disorder. The study poses little risk to participants and offers the potential of substantial benefit. There is essentially no risk above those of normal daily living associated with the incentives, or with the data collection procedures in this study.

b. Steps taken to minimize the risks.

To protect confidentiality, all research participants are identified by participant identification codes (Participant IDs) consisting of their initials and sequentially-assigned participant numbers on most forms and data files, and not by their names. All research data are stored in locked areas accessible only to research staff and are not left unattended. Documents with confidential information are shredded before being discarded. Confidential information is never given to anyone outside of the research program without the explicit written permission of the research participant. Only selected designated staff members are approved to give confidential information out after obtaining explicit written permission from the participant. All research staff are trained in these procedures. We collect only general information about participant activities, legal and illegal. We do not collect information about specific illegal acts. Finally and importantly, the study smartphone app that will be used to provide monitoring and incentives has features that promote compliance with HIPAA.

Date: April 12, 2023

Principal Investigator: [name]

Application Number: IRB00220692

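### The one explicit stopping criterion counts only related adverse events, no by-group safety table is scheduled and the anticipated event rate is not stated, so an excess in one group could go unflagged by that criterion

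*Combined protocol and SAP*

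**What the plan says.** Section 7.d (Early stopping rules) has these elements:

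- **Case review:** "At least one investigator will review each adverse event as it occurs".
- **Scheduled DMC review:** "The DMC will review a summary of adverse events annually". The content and layout of the summary are not described.
- **Trigger for more frequent review:** "This frequency of review will be increased if the adverse events occur at a higher rate than anticipated".
- **Discretionary stopping:** a separate sentence lets the trial be stopped on a recommendation of the investigators or the DMC. It sets no relatedness limit and no criterion.
- **Explicit criterion:** investigators and DMC are asked to recommend stopping if the review suggests to any one of them that "the number of related adverse events is unacceptably high". Neither related nor unacceptably high is defined.
- **Group comparison:** "The investigators or DMC will be allowed to request statistical analyses to compare the groups on the rates of different adverse events". This is a permission and is not scheduled.

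The heading of section 8.a calls for "listing all procedures, their major and minor risks and expected frequency". The text beneath it gives no frequency. It says instead: "There is essentially no risk above those of normal daily living associated with the incentives, or with the data collection procedures in this study".

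**The concern.** Contingency management is a behavioural intervention that the protocol itself describes as nearly free of risk. When an overdose, a death or a suicidal episode in a person with opioid use disorder is reviewed alone, the underlying disorder offers an obvious explanation other than the study. Attribution case by case is therefore a weak filter for such events. If the intervention did affect them, in either direction, the effect would show mainly as a difference between randomised groups, and no by-group display is scheduled.

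The question follows from the protocol's own Background (section 3). It says that some patients relapse once incentives end and that mortality rises after treatment stops. Here incentives end at 3 months and follow-up runs for 9 more.

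The listed outcomes do not fill the gap. Section 2 names reduction of overdose as a secondary aim, but the matching variable in section 7.b is a total score for overdose risk behaviours, not a count of overdoses. The suicide and overdose measures in section 8.b (screening question, escalation, referral, pamphlet) act on the individual and are not trial-level rules.

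At stake is whether an imbalance in serious events would be put before the DMC routinely, or only if someone thought to ask for the comparison.

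**Working it through.** **1. Can the rules be evaluated as written?** The plan states no adverse-event figure to reproduce. The documents contain no rate or threshold for adverse events, overdose, death or suicidality, so the operating characteristics of the stopping criterion and of the review trigger cannot be computed. The only figure taken from the plan below is 125 participants per group, 375 in total (section 7.c). Everything else is assumed, for illustration.

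**2. The related-only count.** If a share f of the events in a group is judged related, N events add f × N to the criterion. With f = 0 the contribution is 0, whatever N is.

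Assumed counts of 10/125 in one Contingency Management group and 2/125 in Usual Care give a two-sided Fisher exact p = 0.034. The criterion's count at f = 0 is 0 against 0. The p-value is sensitive to a single event: 9 against 2 gives p = 0.060. No allowance is made for three groups or repeated looks.

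**3. The review trigger.** It is not limited to related events. Its weakness is the missing reference rate, and the plan does not say whether the rate is read per group or pooled. If it is pooled, and the background risk p is multiplied by RR in one of three equal groups, then

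pooled rate ÷ p = (2 + RR) / 3

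RR = 2 gives 4/3, a rise of 33%. RR = 3 gives 5/3, a rise of 67%.

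The table assumes p = 2%, 5% or 10%. The pooled check is an exact one-sided 5% test of the total in 375 against p, treating p as known; it fires at 13, 27 and 48 events respectively. The group comparison is a two-sided 5% Fisher test of 125 against 125.

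| Assumed p | RR | Expected events, background vs raised group | P(pooled check fires) | Fisher power |
|---|---|---|---|---|
| 2% | 2 | 2.5 vs 5 | 0.206 | 0.066 |
| 2% | 3 | 2.5 vs 7.5 | 0.482 | 0.237 |
| 5% | 2 | 6.25 vs 12.5 | 0.368 | 0.235 |
| 5% | 3 | 6.25 vs 18.75 | 0.815 | 0.698 |
| 10% | 2 | 12.5 vs 25 | 0.644 | 0.538 |
| 10% | 3 | 12.5 vs 37.5 | 0.986 | 0.975 |

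Two things follow. Even with the anticipated rate known exactly, a pooled trigger would often stay silent when risk doubles in one group. And a by-group table is not a more powerful test: its power is lower in every row, because the background rate must be estimated from the comparator. Its gain is that it needs no prior rate and shows which group carries the excess.

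**4. Timing.** Section 3 plans the trial over 4 years. Assume even accrual over 3 of them: 375 / 3 = 125 per year. Those randomised in the first 9 months of a review year have finished the 3-month intervention by the annual review: 125 × 9/12 = 93.75, or 75%. The percentage rests on even accrual within the year, which the documents do not state. It ignores investigator review of each event and the option to review more often.

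**The case against.** The strongest reply is that only one sentence in section 7.d uses the word related. The sentence before it allows stopping on a recommendation with no such limit, and any single investigator or DMC member can prompt the explicit one. Staff must report any sign of an adverse event, and participants in every group are asked about every type of event at each scheduled assessment. The DMC summary and the review trigger carry no relatedness filter, and unanticipated problems also go to the IRB (section 8.c). A judgement-based rule is a legitimate choice for a low-risk behavioural trial. All of this stands, and it rules out several stronger readings that a reader might infer:

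- **That the trial cannot be stopped for unrelated events, or that monitoring is absent.** The discretionary sentence and the all-event collection contradict this.
- **That the trial could not conclude on safety at the end.** An interim criterion does not restrict final reporting, and the events are collected in all groups.
- **That investigators will judge these events unrelated because they know the group.** Section 4.c says only that participants are unblinded; it is silent on investigators. The statement in section 8.a is about risk and is not an attribution rule.
- **That overdose, death and suicidality are known to be frequent among those enrolled.** The documents give no such rate.
- **That 10 against 2, or 75%, estimates what will happen.** Both are illustrations on assumed inputs.

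What the reply does not remove is that the discretionary power has no criterion, the comparison has no schedule and the trigger has no reference value. A DMC charter might supply these, but the documents neither include nor cite one.

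**Conclusion.** The concern holds in a limited form. The explicit criterion is confined to related events, the annual summary is unspecified, group comparison is on request only, and the anticipated rate is stated nowhere. An excess of overdoses, deaths or suicidality in one group, judged unrelated case by case, could therefore go unflagged by the stated criterion, although discretion to stop remains.

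No size can be derived from the documents. Under the assumed risks of 2% to 10%, a doubling in one group would trip a pooled check with probability of about 0.21 to 0.64, so silence is plausible, most clearly when events are rare. The conclusion itself rests on the text and on the possibility that such events are judged unrelated; it does not depend on the illustrative figures. This is a specific and inexpensive gain in safety monitoring and should be made.

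**What to change.** Amend section 7.d as follows:

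1. Every scheduled DMC summary tabulates all adverse events by randomised group with person-time, whatever their attributed relatedness. At a minimum it shows deaths, overdoses, suicidal ideation or attempts, and hospitalisations. Usual Care is the concurrent comparator, and relatedness is an extra column.
2. The stopping criterion is worded so that the DMC's review is not confined to related events.
3. The anticipated rate behind the review trigger is stated by event type, with a note on whether it is read per group or pooled. It is kept alongside the group comparison as an absolute check. Replacing it with Usual Care would hide an excess shared by all three groups.

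The decision to stop, and any threshold, stay with the DMC.

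The cost is amendment wording and a by-group table. Adverse events are already asked about at each assessment in every group. The downside is small: chance imbalances will be shown and need interpretation, and power for rare events is low, so the table should inform the DMC's judgement and not serve as a formal test.
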